### **12.3 Source Documents**

To standardize the collection of study data, the CLO will provide the PO's with protocol specific Visit Guides and Source Document Worksheets to ensure that all required data elements are captured. These documents will be used to supplement data collected on primary clinical source documents. All data reported must be documented either on a separate source document found in the participant's medical record or on the Visit Guides and Source Document Worksheets. All source documents must be signed by the study team member that collected or elicited the information in the source documents. Source documents will be submitted to the CLO (either by fax, or e-mail) for entry into the OnCore database within 10 business days of each study contact. Primary clinical source documents will be de-identified and relabeled with the participant's PID number prior to submission. Documents containing participant personally identifiable information that has not been completely obscured cannot be accepted and will be returned to the site.

### **12.4 Data and Safety Monitoring Plan**

All of the procedures outlined in the University of Wisconsin Chemoprevention Consortium standardized Data and Safety Monitoring Plan (approved 03/20/2018) as well as the Master Data and Safety Monitoring

Plan will be followed in this protocol. The UW Chemoprevention Consortia Data and Safety Monitoring Committee meet every 6-12 months to review all data from ongoing consortium studies.

## **12.5 Sponsor or FDA Monitoring**

The NCI, DCP (or their designee), pharmaceutical collaborator (or their designee), or FDA may monitor/audit various aspects of the study. These monitors will be given access to facilities, databases, supplies and records to review and verify data pertinent to the study.

## **12.6 Record Retention**

Clinical records for all participants, including CRFs, all source documentation (containing evidence to study eligibility, history and physical findings, laboratory data, results of consultations, *etc.*), as well as IRB records and other regulatory documentation will be retained by the Investigator in a secure storage facility in compliance with Health Insurance Portability and Accountability Act (HIPAA), Office of Human Research Protections (OHRP), Food and Drug Administration (FDA) regulations and guidance, and NCI/DCP requirements, unless the standard at the site is more stringent. The records for all studies performed under an IND will be maintained, at a minimum, for two years after the approval of a New Drug Application (NDA). For NCI/DCP, records will be retained for at least three years after the completion of the research. NCI will be notified prior to the planned destruction of any materials. The records should be accessible for inspection and copying by authorized persons of the Food and Drug Administration. If the study is done outside of the United States, applicable regulatory requirements for the specific country participating in the study also apply.

## **12.7 Cooperative Research and Development Agreement (CRADA)/Clinical Trials Agreement (CTA)**

Not Applicable

## **13. STATISTICAL CONSIDERATIONS**

### **13.1 Study Design/Description**

This is a multi-center, phase IIA, single-arm ‘window of opportunity’ pilot study of 25 mg per day exemestane for 21 to 42 days in patients undergoing planned surgery for CAH/EIN or low grade endometrial cancer, with an age, disease and BMI-matched comparator cohort, obtained from each institution’s biobank,

We plan to enroll up to 40 patients over 12-18 months at an accrual rate of 2-3 patients per month. Although all subjects will have CAH/EIN or low grade endometrial cancer based on their referral biopsy, we anticipate that some subjects will not have CAH/EIN or low grade endometrial cancer on central pathology review, thus making them ineligible for final analysis. Additionally, tissue samples may not be adequate for measuring Ki-67 expression. We therefore anticipate that approximately 25% of subjects will not be eligible for final analysis. This will result in 30 evaluable patients, the effective sample size for the study.

### **13.2 Randomization/Stratification**

In the absence of randomized placebo controls, we will obtain age, disease and BMI matched comparator cohort from each institution’s biobank. The historical samples from each matched control will need to be obtained within 42 days of each other in order to be consistent with the study participants. This matching will be one-to-one. A comparison of Ki-67 expression between subjects on this study and historic controls is not a primary goal of the study. The primary outcome is the overall change in Ki-67 expression between pre and post-treatment of each subject. The reason a historic cohort will be studied is to provide the context in which to assess the effects of exemestane in reducing Ki-67 from baseline to post-exposure to

exemestane. Specifically, there may be a change in Ki-67 expression from pretreatment biopsy to final surgical specimen in the historical control cohort suggesting that time alone (between biopsy and surgery) or potentially differences in tissues acquisition (biopsy versus surgical specimen) may have an impact on Ki-67 expression.

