For Site in Italy: 
 
1. Prescreening visit: 
 
- Before the diagnostic hysteroscopy, participants will sign a biopsy consent
 
- During the exam, gynecologist will perform the double pass biopsy (one pass for diagnosis and one for research).
 
 
 
2. Screening/pre-baseline visit (day 0): 
 
- If CAH/EIH or low grade endometrial cancer confirmed, participants will sign the main study consent
 
- Perform lab tests for eligibility requirement assessment.
 
- Tampon will be placed by a study nurse.
 
- Send eligibility documents to Consortium Lead Organization (CLO) for eligibility confirmation.
 
 
 
3. Baseline visit (day 1): 
 
- During clinic visit the tampon will be collected
 
- Study drug dispensed.
 
- Establish date of surgery
 
 
 
	For Sites in USA: 
 
1. Prior to baseline (pre-surgical) clinic visit 
 
- Pre-Screening by record review/introductory telephone contact
 
- If interested, mail screening consent packet and 2 tampons
 
- Phone call reminder the day before baseline (pre-surgical) clinic visit to place tampon before visit
 
 
 
2. Baseline (pre-surgical) clinic visit (minimum of 22 days prior to planned surgery) 
 
- Obtain written consent
 
- Perform baseline tests and procedures (including tampon removal and biopsy)
 
- Establish date of surgery
 
 
 
3. Confirm eligibility 
 
- Send via courier exemestane with start date instructions and pill diary
 
- Also, send a tampon kit (2 tampons + instructions); tampon to be inserted 8-12 hours before surgery
 
 
 

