Because this is a window of opportunity study, the study period will be limited to the time between the initial pre-surgical visit and definitive surgery (hysterectomy). In order to reduce number of visits for the study participants and to start treatment in a timely fashion, all eligibility tests will be performed at the baseline (pre-surgical) clinic visit. Being able to acquire an adequate endometrial biopsy specimen is an important part of eligibility given that the primary endpoint of this study compares Ki-67 expression between pre and post treatment tissue. Therefore, an endometrial biopsy for research purposes will be performed at the baseline (pre-surgical) clinic visit during the standard pelvic exam. Laboratory tests will also be performed at the baseline (pre-surgical) clinic visit, either before or after the physical exam and endometrial biopsy. The vaginal tampon, which was inserted by participant prior to the baseline (pre-surgical) clinic visit, will be removed during the pelvic exam. If the participant is subsequently deemed ineligible (either due to inadequate biopsy tissue, laboratory values or physical exam results), the endometrial biopsy samples of the participant will be destroyed and her tampon will be destroyed.

Although attempts will be made to contact all participants prior to their baseline (pre-surgical) visit, the study can also be presented at their baseline (pre-surgical) visit. If interested, the participants will sign the consent form and then undergo study procedures (research biopsy, lab tests, etc) on the day of their baseline (pre-surgical) visit. In this case, participants will not have a tampon sample collection as part of their baseline (pre-surgical) visit. This will not be considered a protocol deviation. If participants are willing to return for an additional visit, they will be permitted to return for a biopsy and tampon collection within 1-2 weeks of signing consent form.

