The study participants will be matched with a historical nonrandomized control group based on age ( $\pm$  5 years), disease type and BMI ( $>20-24$ ,  $25-30$ ,  $>30$ ). Historical samples (no more than 5 years old) will be identified through pathologic databases that exist at all participating sites. Medical records will be reviewed to ensure correct matching. The pre-surgical and post-surgical tissue samples, within 42 days of each other, will be obtained from each historical subject. All subjects will be de-identified. IHC analysis of Ki-67 expression will be performed on the pre-surgical and post-surgical samples.

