#### **5.1 Dose Regimen and Dose Group**

Exemestane 25 mg per day is taken by mouth once a day (participant self-administers) for at least 21 days but not to exceed 42 days prior to surgery. The last dose is taken on the day before surgery.

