#### **5.2 Exemestane Administration**

Exemestane will be dispensed by an investigational pharmacist or appropriate study staff at the participating organization (PO) and then self-administered by the participant at home. Depending on when the surgery is scheduled, the participant will be given 1 or 2 bottles of the study agent. Each bottle contains 30 tablets of exemestane. After confirmation of eligibility, the agent will be mailed to the participants via courier.

Exemestane is a 25 mg tablet to be taken by mouth following a meal once daily at approximately the same time each day. If the dose is missed by more than 8 hours, the patient will skip that dose and take the next scheduled dose at the usual time.

The patient will be provided with a daily pill diary to record the time of administration, side effects, and any missed doses. The patient will be instructed to bring the pill diary and study drug bottles (including any empties) on the day of surgery.

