### **8.2.7 Comparison of Ki-67 expression changes between subjects and a historical cohort**

The reason a historic cohort will be studied is to provide the context in which to assess the effects of exemestane in reducing Ki-67 from baseline to post-exposure to exemestane. Specifically, there may be a change in Ki-67 expression from pretreatment biopsy to final surgical specimen in the historical control cohort suggesting that time alone (between biopsy and surgery) or potentially differences in tissues

acquisition (biopsy versus surgical specimen) may have an impact on Ki-67 expression.

The study participants will be matched with a historical nonrandomized control group based on age (+/- 5 years), disease type and BMI (>20-24, 25-30, > 30). This control group will provide a reference for how Ki-67 may change based on time (specifically time between biopsy and surgery which has to be within 42 days) or differences in specimen collection (endometrial biopsies versus surgical specimen), independent of exemestane exposure.

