#### **8.3 Off-Agent Criteria**

Participants may stop taking exemestane for the following reasons: completed the protocol-prescribed intervention, AE or serious adverse event (SAE), noncompliance, contraindicated medications, medical contraindication or surgery is not performed within 21 to 42 days of the first dose of exemestane. Any participant discontinuing exemestane prior to 1 day before surgery will be instructed to bring the exemestane bottles and the completed pill diary to her next appointment. A final study visit will occur at the participant's first post-surgical visit.

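### The 42-day limit on historical controls is the participants' first-dose-to-surgery maximum, not their biopsy-to-surgery interval, which may be 22 to 73 days at US sites

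*Combined protocol and SAP*

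**What the plan says.** Three sections set the rule for controls. Section 3 states: "The pre-surgical and post-surgical tissue samples, within 42 days of each other, will be obtained from each historical subject". Section 8.2.7 describes the reference as being for change over time, "specifically time between biopsy and surgery which has to be within 42 days". Section 13.2 gives the reason for the limit: the paired samples "will need to be obtained within 42 days of each other in order to be consistent with the study participants". No section sets a minimum interval. Matching is one-to-one on age, disease type and BMI.

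For participants, the same number appears with a different starting point. Section 5.1 has exemestane taken "for at least 21 days but not to exceed 42 days prior to surgery", and section 8.3 lists as a reason for stopping that "surgery is not performed within 21 to 42 days of the first dose of exemestane". Section 3 defines Day 1 as the first day of drug and places surgery on Days 22 to 43.

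The pre-treatment Ki-67 sample is the research biopsy. For US sites, section 3 says that "an endometrial biopsy for research purposes will be performed at the baseline (pre-surgical) clinic visit during the standard pelvic exam". The schedule in section 7.1 allows that visit from Day -30 to Day 0, and section 7.3 asks for its procedures within 30 days of starting drug. Section 5.2 adds: "After confirmation of eligibility, the agent will be mailed to the participants via courier".

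Objective 8 in section 1.2 gives the control group two purposes: to show how Ki-67 changes, without exemestane, with specimen type and with time between biopsy and surgery. Section 13.4 commits to evaluating the participants' change relative to the change in this cohort.

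**The concern.** The stated justification does not hold on the protocol's own schedule. Controls are limited on biopsy-to-surgery time, whereas the participants' 42 days runs from first dose to surgery and leaves out the days between biopsy and first dose. Because the control limit has no floor, it also admits intervals shorter than any the US schedule allows.

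The study has a single arm, so this cohort is its only untreated comparison. If participants tend to have longer intervals than their controls, a difference in Ki-67 change between the groups cannot be separated from a difference in elapsed time. The protocol itself names elapsed time as a possible influence on Ki-67. Nothing in the matching or the analysis plan corrects for this.

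**Working it through.** **Inputs**
- Day 1 is the first dose; surgery is on Day 22 to 43 (section 3).
- US research biopsy: Day -30 to Day 0 (section 7.1), or no more than 30 days before Day 1, which is Day -29 (section 7.3).
- Controls: at most 42 days between samples, no minimum (sections 3, 8.2.7 and 13.2).

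**Where 42 comes from.** First dose to surgery is surgery day minus 1: 22 - 1 = 21 to 43 - 1 = 42 days. This reproduces the 21 to 42 days in sections 5.1 and 8.3.

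**Biopsy to surgery, US participants.** Interval = surgery day minus biopsy day.
- Shortest: 22 - 0 = 22 days. The schema agrees, requiring the baseline visit at least 22 days before planned surgery.
- Longest: 43 - (-30) = 73 days by section 7.1; 43 - (-29) = 72 days by section 7.3.
- Exclusion 4.2.2 words the surgery limit as 43 days from starting drug. Read as 43 elapsed days (Day 44), the longest interval is 44 + 30 = 74 days.

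None of these readings gives 42 as the maximum.

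**Permitted ranges compared**

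| Interval (days) | Controls | US participants |
|---|---|---|
| 0-21 | allowed | not possible |
| 22-42 | allowed | allowed |
| 43-73 | not allowed | allowed |

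The largest excess over the control limit is 73 - 42 = 31 days (72 - 42 = 30 by section 7.3). Within a pair, participant minus control can run from 22 - 42 = -20 to 73 - 0 = +73 days.

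**How easily the limit is passed.** With a biopsy L days before Day 0, the interval is surgery day + L. It exceeds 42 when the surgery day is 43 - L or later.

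| Biopsy day | First surgery day over 42 days | Permitted surgery days affected |
|---|---|---|
| 0 | 43 | 1 of 22 |
| -7 | 36 | 8 of 22 |
| -14 | 29 | 15 of 22 |
| -21 | 22 | 22 of 22 |

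There are 31 permitted biopsy days and 22 permitted surgery days, so 31 × 22 = 682 combinations. Those within 42 days number 21 + 20 + … + 1 = 231, or 231/682 = 34%. This counts permitted schedules. It does not forecast actual ones.

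**Italy.** The research biopsy is taken at the pre-screening hysteroscopy, before diagnosis. The documents do not say whether the 30-day limit in section 7.3 covers it. Section 4.1.1 requires the diagnostic pathology report to be within 45 days of the baseline visit, but describes that report as coming from the referring facility. Assuming that limit applies and dates from the biopsy, a Day 1 baseline visit puts the earliest biopsy on Day 1 - 45 = -44, an interval of 43 + 44 = 87 days. A Day -30 baseline visit would give 43 + 75 = 118 days.

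**The case against.** The strongest objection concerns weight. Section 13.2 says that the comparison is not a primary goal and offers it as context. The documents say only that Ki-67 may change with time and give no untreated rate, so no bias is demonstrated. The 73-day figure is an extreme: section 3 combines the eligibility tests in one visit so that treatment starts promptly, and with a Day 0 biopsy only Day 43 surgery exceeds the limit, by one day. Sections 3 and 7.3 also let US participants return for the biopsy after signing consent, which can bring it closer to Day 1. All of this stands. It limits how large the problem may be in practice, but it does not make 42 days the participants' interval.

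Second, the wording in section 8.2.7 could be read as limiting participants to 42 days as well. The visit windows do not enforce such a limit, and Day 43 surgery would always break it. If that was the intent, the sections contradict each other and must be reconciled.

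Third, a spread of control intervals is itself informative about change over time, and narrower limits remove some of it. That is fair, but controls at 0 to 21 days describe intervals no scheduled US participant has, while none describe 43 to 73. Limits alone would also leave mismatch within pairs, and with about 30 pairs any restricted analysis will be small. These are reasons to match where possible, report the intervals, and treat further analyses as supportive.

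**Conclusion.** The concern holds. The 42-day limit is not consistent with the participants' Ki-67 interval, and the reason given in section 13.2 is incorrect. Permitted intervals are 0 to 42 days for controls and 22 to 73 days for US participants (72 to 74 at the top under other readings), with 22 to 42 shared and no matching on interval. The comparison therefore does not reliably serve its purpose of showing change due to time. Its specimen-type purpose, the primary one-sample test and the power calculation are unaffected.

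These are limits set by the text and assume surgery within the scheduled days. The documents do not give typical biopsy timing, so actual gaps may be much smaller. The size and direction of any bias cannot be derived. The change should be made, but the validity of the primary analysis does not depend on it.

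**What to change.** 1. In sections 3, 8.2.7 and 13.2, replace the 42-day rule for controls by a lower and an upper limit on the interval from the biopsy used for Ki-67 to surgery. Take both limits from the observed intervals of evaluable participants and fix them before any control Ki-67 is read. Correct the stated reason in section 13.2.
2. Where the archive allows, also match on interval within a stated tolerance. Seven days is an example, not a figure from the documents.
3. Report the interval distribution in both groups beside the comparison in section 13.4. Add a sensitivity analysis of pairs in which both intervals lie in the shared range.
4. Treat any interval-adjusted regression as supportive only. A participant's interval includes her time on drug, so the model must state its assumption that Ki-67 changes with interval at the same rate in both groups.
5. State which biopsy-timing limit applies to the Italian research biopsy. Reconcile the 43-day wording in exclusion 4.2.2 with the 21 to 42 days in section 8.3.

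The cost is wording in the sections named, one descriptive table and one sensitivity analysis. The timing is workable: section 10.1.1 ships control blocks and slides at the end of the study and forbids cutting slides before shipment, although the documents do not say when controls are selected. The drawback is that some archived controls become ineligible, on top of the age, disease, BMI and 5-year limits, and the documents do not show how many would remain. If too few remain, apply the new limits without tolerance matching.

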### 13.3 Accrual and Feasibility

Each participating organization sees over 100 new patients annually with diagnosis of CAH/EIN or low grade endometrial carcinoma. It is planned to enroll up to 40 participants over 12 to 18 months from the three participating clinical sites to ensure 30 evaluable patients.

### 13.4 Primary Objective, Endpoint(s), Analysis Plan

The primary objective is to determine if there is a decrease in proliferation index, measured by percent Ki-67 expression, in CAH/EIN or low grade endometrial cancer cells from baseline to post-exposure. Therefore, the primary endpoint is the absolute change in Ki-67 expression in endometrial cancer cells from baseline to post-exposure. We will evaluate the change from baseline to post-exposure in absolute change in Ki-67 using one-sample Student's t-test or Wilcoxon signed-rank test, as appropriate. In addition, we will evaluate the change relative to the change recorded in the historic cohort.

Ki-67 values for patients with endometrial cancer are available in prior research. When the patients from this paper are limited to those with low grade cancers, the mean (standard deviation) of the decrease from baseline was 7.2 (7.5) among the treated patients. Given an SD of 7.5, the table below shows the detectable effect sizes (defined as the mean change divided by the standard deviation of the change) and mean changes for a one-sided test for significance level  $\alpha=0.05$  and various power ( $1-\beta$ ) levels for the primary endpoint given the effective sample size of 30. For example, using an 0.05 level one-sided one-sample Student t-test, we would be able to detect an effect size of 0.50, which corresponds to a mean decrease of 3.8, with 0.85 power.

	Power		
	0.80	0.85	0.90
Effect Size	0.46	0.50	0.55
Mean Decrease	3.5	3.8	4.1

The mean decreases in this table are smaller than the mean difference in the treatment group for those with low grade endometrial cancer in the prior research with letrozole. We are including CAH/EIN in addition to low grade endometrial cancer in the current study and therefore it is not unreasonable to expect a lesser treatment effect for these patients with a less severe form of the disease. For these reasons, we feel there is a need to power for smaller differences.

It is estimated that 50% of the patients will have CAH/EIN and 50% will have low grade endometrial cancer. For subgroups each with 15 patients, using a 0.05 level one-sided one-sample Student t-test, and assuming the same standard deviation as above, there will be power of 0.8-0.9 to detect a mean decrease ranging from 5.1-6.0. Because of the nature of the study being exploratory, we are not making adjustment for multiplicity of testing in subgroups defined by CAH/EIN vs low grade carcinoma.

